1.1 Clinical Studies

The safety, pharmacokinetics (PK), and pharmacodynamics (PD) of SKI-O-703 have been evaluated in 2 clinical studies, a single ascending dose study (OSCO-P1201) and a multiple ascending dose study (OSCO-P1202) in healthy subjects.

[figure not shown]
Safety

[figure not shown]
In Study OSCO-P1201, single oral doses of SKI-O-703 ranging from 50 to 800 mg were generally safe and well tolerated by the healthy male and female subjects. There were no deaths, serious adverse events (SAEs), or treatment-emergent adverse events (TEAEs) that led to discontinuation of the study. Ten of 48 subjects (20.8%) reported a total of 18 TEAEs; of these, 3 TEAEs were reported by 3 subjects (25.0%) after receiving placebo and 15 TEAEs were reported by 7 subjects (19.4%) in the SKI-O-703 treatment groups. There were no dose-dependent trends noted in the TEAEs reported. The most commonly reported TEAE after receiving SKI-O-703 was headache, which was reported by 3 subjects (8.3%) who received SKI-O-703 and 1 subject (8.3%) who received placebo. All TEAEs across the

50- to 600-mg dose range were considered mild in intensity; 6 treatment-related moderate-intensity TEAEs, reported in 2 subjects, occurred at the highest dose of 800 mg SKI-O-703. All TEAEs resolved by the end of the study. All individual hematology and coagulation, serum chemistry, and urinalysis values outside of the reference ranges were considered not clinically significant by the investigator. No TEAEs related to laboratory parameters were reported.

[figure not shown]
In Study OSCO-P1202, multiple oral doses of SKI-O-703 200 mg once daily (QD), 400 mg QD, and 200 mg twice daily (BID) were safe and well tolerated by the healthy male and female subjects. There were no deaths or SAEs; however, 1 subject reported TEAE of back pain that led to discontinuation of 200 mg SKI-O-703 BID. Overall, 7 subjects (29.2%) reported a total of 17 TEAEs; of these, 2 subjects (33.3%) reported 6 TEAEs after receiving placebo and 5 subjects (27.8%) reported 11 TEAEs after receiving SKI-O-703. The most commonly reported TEAEs were nausea and headache, each were reported by 2 subjects (33.3%) in the 200 mg SKI-O-703 BID treatment group and by 1 subject (16.7%) in the placebo group. All TEAEs were considered mild or moderate in intensity, and both moderate TEAEs occurred in the placebo group. Except for 1 subject who reported ongoing TEAEs of pyuria and chlamydial infection, all TEAEs resolved by the end of the study. No apparent treatment- or dose-related trends were observed in clinical laboratory values, physical examination findings, or 12-lead electrocardiogram (ECG) results. There was a slight trend in the mean increase of systolic blood pressure from baseline in the 200 mg BID group at Days 16 and 21, and diastolic blood pressure values at Days 16 and 21 also demonstrated a slight trend of a mean increase for all doses of SKI-O-703. There were no significant changes in systolic and diastolic blood pressure for all doses of SKI-O-703 versus placebo at Days 16 and 21.

Pharmacokinetics

[figure not shown]
Pharmacodynamics

[figure not shown]

1.2 Nonclinical Studies

[figure not shown]
1.2.1 Pharmacology, Pharmacokinetics, and Toxicology Summary

Nonclinical Pharmacology

[figure not shown]

[figure not shown]

Nonclinical Pharmacokinetics and Toxicokinetics

Nonclinical Toxicology

1.3 Dose Rationale

SKI-O-703 was safe and well-tolerated in healthy volunteers when administered as single ascending doses over the dose range of 50 to 800 mg (Study OSCO-P1201), and multiple ascending doses at 200 mg QD, 400 mg QD and 200 mg BID for 7 days (Study OSCO-P1202). Based on the safety data from the various doses administered in these studies, there are no specific considerations that would concern the use of SKI-O-703 at doses proposed in this Phase 2 study.

Following multiple ascending doses of SKI-O-703 at 200 mg QD, 400 mg QD, and 200 mg BID (Study OSCO-P1202), a reduction in the PD endpoint “percentage of basophils expressing CD63+” was observed in healthy volunteers; on average, CD63+ expressing basophils were suppressed by 95%, 99% and 86% at steady state (Day 7) following administration at 200 mg QD, 400 mg QD, and 200 mg BID, respectively. Thereafter, the

suppression of basophils expressing CD63+ was maintained at 72% or below for up to 2 and 8 hours following once-daily dosing at 200 mg and 400 mg, respectively, and up to 12 hours (ie, over a full 24-hour period) following twice-daily dosing at 200 mg. As the maximum PD response was very similar across all 3 of these dosing regimens, a wider dose range (100 mg to 400 mg BID) has been selected in this Phase 2 study to fully explore changes in PD markers over a wider range, and, as the PD effect was sustained for longer after twice-daily dosing compared to once-daily dosing, twice-daily dosing has been selected.

As 400 mg BID has not been studied previously in humans, exposure (C_{max} and AUC_{0-tau}) to SKI-O-592, M2, and M4 following 400 mg BID dosing has been estimated based on data observed previously at different dose levels. To ensure that predictions are cautious and robust, steady-state C_{max} and AUC_{0-tau} following 400 mg BID have been predicted in 2 ways using data from Study OSCO-P1202:

1. AUC_{0-12} (400 mg, Day 1) \times Accumulation Ratio (200 mg BID)
2. PK Parameter (200 mg BID, Day 7) \times 2

Systemic exposure (C_{max} and AUC_{0-tau}) to SKI-O-592, M2, and M4 at 400 mg BID is predicted to be higher using the second approach [PK Parameter (200 mg BID, Day 7) \times 2]. For SKI-O-592, C_{max} and AUC_{0-tau} are predicted to be 6160 ng/mL and 14600 h \cdot ng/mL, respectively, and for M2 C_{max} and AUC_{0-tau} are predicted to be 994 ng/mL and 10000 h \cdot ng/mL, respectively, which is well within exposure levels calculated at the NOAEL in rats, and comparable to levels previously observed at 800 mg in Study OSCO-P1201. However, due to the very low M4 metabolite ratios (R_{met}) observed in rats compared to healthy volunteers, predicted exposure to M4 (644 ng/mL and 1970 h \cdot ng/mL for C_{max} and AUC_{0-tau} , respectively) is higher than the NOAEL exposure. Therefore, the dosing regimens proposed for this study (100 mg BID, 200 mg BID, and 400 mg BID) have been carefully selected to ensure that exposure to M4 does not exceed levels observed previously in healthy volunteers (Study OSCO-P1201, 800 mg).

Note: Because increases in systemic exposure to M4 were less than proportional to the dose of SKI-O-703 in Studies OSCO-P1201 and OSCO-P1202, and a reduction in M4 levels was observed over time in Study OSCO-P1202, both means of estimating C_{max} and AUC_{0-tau} for M4 at 400 mg BID are considered to be cautious approaches, potentially overestimating exposure at 400 mg BID.

Following single oral administration of 400 mg SKI-O-703 (Study OSCO-P1203), overall systemic exposure to SKI-O-592, M2 and M4 (AUC_{0-t} and AUC_{0-inf}) was comparable between the fed and fasted state, with 90% CI for the ratio (Fed/Fasted) contained entirely within the BE limits (0.80, 1.25) for SKI-O-592 and M4. By contrast, when administered in the fed state there was an approximate 56%, 43% and 46% reduction in maximum exposure (C_{max}) for SKI-O-592, M2 and M4, respectively, with an associated 2.5 to 4 hour delay in median t_{max} across all analytes. Since the overall extent of absorption is unaffected by the intake of food, but peak exposure is reduced, dosing is recommended with food in this Phase 2 study to reduce the potential for AEs which may be associated with spikes (ie, high C_{max}) in SKI-O-592, M2 and M4.

1.4 Placebo Rationale

The proposed study is a placebo-controlled, double-blind study of oral SKI-O-703 coadministered with background therapies for RA. The double-blind, placebo-controlled, randomized clinical study design is considered the gold standard for the safety and efficacy assessment of a new therapy both by clinicians and regulatory authorities. In this study subjects will be allowed to receive background medications for RA, including MTX, and other oral DMARDs, therefore subjects are also allowed to receive permitted concomitant medications in line with current standard of care (SOC) practices for RA. Any subject who cannot adhere to the protocol or who discontinues treatment will have an end-of-treatment (EOT) and will be followed for the intended duration of the study.

1.5 Benefits and Risks Assessments

In the clinical development program, the safety, tolerability, and PK of SKI-O-703 have been evaluated in 2 clinical studies, a single ascending dose study (OSCO-P1201) and a multiple ascending dose study (OSCO-P1202) in healthy subjects. No deaths and SAEs were reported in these studies; however, 1 subject reported TEAE of back pain that led to discontinuation of SKI-O-703. All AEs were mild to moderate in intensity.

The identified potential risks associated with SKI-O-703 were formulated based on nonclinical data and the SKI-O-703 mechanism of action, and include immune system effects, gastrointestinal effects, liver enzyme changes, and cardiovascular effects. Based on the clinical information received from Study OSCO-P1201 and Study OSCO-P1202, the risk of gastrointestinal effects was updated and headache was included as an important potential risk.

The information is in line with the expected side effects of treatment with SKI-O-703. The proposed safety monitoring is deemed to be sufficient to monitor potential risks of SKI-O-703 administration.

Based upon the nonclinical and clinical evidence highlighted above, the benefits of the conduct of the proposed clinical study outweigh the associated risks.

2 Study Objectives

2.1 Primary Objective

The primary objective of this study is to evaluate the efficacy of select (100 mg BID, 200 mg BID, and 400 mg BID) doses of SKI-O-703 compared with placebo in subjects with active RA who have had an inadequate response to conventional synthetic disease modifying antirheumatic drugs (csDMARDs) or previous 1, 2 or more anti-TNF α biologic agents.

2.2 Secondary Objectives

The secondary objectives of this study are as follows:

- To evaluate the efficacy on other clinical endpoints of select (100 mg BID, 200 mg BID, and 400 mg BID) doses of SKI-O-703 compared with placebo in subjects with active RA who have had an inadequate response to csDMARDs or previous 1, 2 or more anti-TNF α biologic agents.
- To evaluate the safety and tolerability of select (100 mg BID, 200 mg BID, and 400 mg BID) doses of SKI-O-703 compared with placebo in subjects with active RA who have had an inadequate response to csDMARDs or previous 1, 2 or more anti-TNF α biologic agents.
- To investigate the PK profile of SKI-O-592 (the free base of SKI-O-703) and its metabolites (M2 and M4) in subjects with active RA who have had an inadequate response to csDMARDs or previous 1, 2 or more anti-TNF α biologic agents.
- To evaluate the effects of SKI-O-703 on exploratory PD biomarkers (ie, the percentage of activated gp53/CD63+ basophils in peripheral blood) in subjects with active RA who have had an inadequate response to csDMARDs or previous 1, 2 or more anti-TNF α biologic agents.

2.3 Exploratory Objective

The exploratory objective of this study is as follows:

- To evaluate the PK/PD relationship between plasma concentrations of SKI-O-592, M2, and M4 and the percent change in activated gp53/CD63+ basophils in peripheral blood in subjects with active RA who have had an inadequate response to csDMARDs or previous 1, 2 or more anti-TNF α biologic agents.

3 Investigational Plan

3.1 Study Design

This is a randomized, double-blind, multicenter, placebo-controlled, parallel dose study to evaluate the efficacy, safety, tolerability, PK, and PD of select (100 mg BID, 200 mg BID, and 400 mg BID) doses of SKI-O-703 in subjects with RA who have had an inadequate response to csDMARDs or anti-TNF α biologic agents. The proportion of subjects who have received previous biologics will be dependent on the enrollment metrics for the study since there are geographic factors that may influence this proportion. Ratio will be approximately 70% csDMARDs to 30% biological therapy.

Approximately 148 subjects are planned to participate in 4 cohorts (37 subjects each). Subjects will be randomly assigned using a 1:1:1:1 ratio to receive one of the three doses of SKI-O-703 (100 mg BID, 200 mg BID, or 400 mg BID) or placebo. Dosing will be twice daily for 12 weeks.

A schematic diagram of the overall study design is presented in Figure 3-1.

Figure 3-1 **Study Design Schematic**

Screening Period (up to 28 days)	12-Week Treatment Period (Double-Blind) 1:1:1:1							Follow-up (EOT+14 days)	EOS (EOT+28 days)		
	100 mg BID										
	200 mg BID										
	400 mg BID										
	Placebo BID										
Week	0 ^a	2	4	6	8	10	12	14	16		
Visit	1	2	3		4		5 (EOT)	6	7		

Abbreviation: BID, twice daily; EOT, end-of-Treatment; EOS, end-of-Study

^a randomization

Screening Period

The study will include screening period of up to 28 days. All potential subjects will sign and date the informed consent form (ICF) prior to any study assessments or procedures. Potential subjects will be assessed as per the eligibility criteria at screening. Medical history and concomitant medications will be recorded. After completing all screening assessments, subjects who meet all the inclusion and none of the exclusion criteria will proceed to the treatment period.

Randomization: Study Day 1

On Day 1, the subject should complete the Patient's Global Assessment of Disease Activity, the Patient's Assessment of Pain, and the Health assessment questionnaire before site personnel perform any clinical assessments. These should also be completed before any interaction with site personnel has occurred to avoid biasing the subject's response. After that subject's eligibility will be confirmed and baseline safety evaluations will be performed (12-lead ECG, physical examination, vital sign measurements, weight, urine pregnancy test, and safety laboratory assessment). Following predose study procedures, the subject will be randomly assigned to receive either SKI-O-703 or placebo. On Day 1, subject will be administered his/her first dose of study medication no later than 30 minutes after food with approximately 8 ounces (240 mL) of water by the site personnel. The study site personnel will check the subject's mouth to ensure the study drug and entire volume of water was swallowed.

A subset of subjects from each cohort who provide additional consent will be subjected to additional PK and PD assessments according to the Schedule of Events (Table 6-1). Due to PD assay limitations, PK and PD sampling will only be performed at selected sites that are deemed suitable to support PK/PD assessment (ie, which are within an acceptable shipping distance from a PD laboratory). Every effort will be made to achieve a minimum of 24 subjects (6 subjects per treatment group) in the PK/PD subgroup. It is important to note that there is no upper limit to the number of subjects that will be enrolled to the PK/PD subgroup in any region (as many subjects will be assigned to the PK/PD subgroup as is practical), and the number of subjects does not need to be identical between treatment groups; however, every effort will be made to ensure that the number of subjects enrolled to each treatment group is similar.

The second dose will be administered approximately 12 hours (± 2 hours) after the first dose. The second dose and all subsequent doses will be self-administered by the subject. The subjects will be instructed to take study medication no later than 30 minutes after food.

12-week Treatment Period

Subjects will return to the clinic for routine safety and disease state review as outlined in the Schedule of Events (Table 6-1), with a ± 3 days window for all visits after randomization. During the visits, the subject will undergo the following procedures at the timepoints specified in the Schedule of Events: vital sign measurements, urine pregnancy test (for WOCBP only), routine safety laboratory sampling, disease state analysis (hsCRP sampling, joint counts, and ACR assessments), IMP accountability and dispensation, 12-lead ECG, concomitant medication review, and AE review.

The subject should complete the Patient's Global Assessment of Disease Activity, the Patient's Assessment of Pain, and the Health assessment questionnaire before site personnel perform any clinical assessments. These should also be completed before any interaction with site personnel has occurred to avoid biasing the subject's response.

4-week Follow-up Period

After the EOT visit, subjects will complete a 4-week follow-up period. The subject will undergo following procedures at the timepoints specified in the Schedule of Events: vital sign and weight measurements, urine pregnancy test (for WOCBP only), routine safety laboratory sampling, disease state analysis (hsCRP sampling, joint counts, and ACR assessments), 12-lead ECG, concomitant medication review, and AE review.

The subject should complete the Patient's Global Assessment of Disease Activity, the Patient's Assessment of Pain, and the Health assessment questionnaire before site personnel perform any clinical assessments. These should also be completed before any interaction with site personnel has occurred to avoid biasing the subject's response.

The maximum duration of study participation for a subject will be 143 days (approximately 20 weeks), which consists of a screening period of up to 4 weeks (28 days), 12 weeks of dosing (84 days), and a 4-week follow-up period (28 days ± 3 days).

3.1.1 Dose Interruption and Reduction

Adverse Events:

It is recognized that some AEs may require dose adjustment or study drug discontinuation. Guidelines for dose reduction are outlined in Table 3-1.

Table 3-1 Guidelines for Dose Interruption and Reduction^a

AE	Occurrence ^b	Action
ALT or AST elevations (range 3 to 5 \times ULN) or ALP $>3 \times$ ULN and $>2 \times$ baseline	First	
 • If asymptomatic (no nausea, anorexia, vomiting), repeat test within 72 hours^c and, if stable or lower, may continue dosing of study drug. • If on repeat test value has increased further but remains $<5 \times$ ULN and asymptomatic, withhold study drug and retest weekly until values becomes stable. When stabilized to $<5 \times$ ULN, continue dosing with the study drug. • If symptomatic or $>5 \times$ ULN, withhold csDMARDs and study drug. Follow the subject weekly until symptoms abate and values return to baseline per confirmation from central laboratory, at which time csDMARDs may be restarted at the prior dose and study drug may be restarted at a reduced dose by skipping one of the doses. 
Note: Discontinue study drug permanently if the ALT elevation is accompanied by an elevation in direct bilirubin to >2 mg/dL (34.2 mmol/L).

	Second	Discontinue study drug permanently.
ANC $<1500/\text{mm}^3$ or $<1.50 \times 10^9/\text{L}$	First	Study drug must be withheld. Repeat the test weekly until value return to baseline or $\geq 1500/\text{mm}^3$ or $\geq 1.5 \times 10^9/\text{L}$, and then restart at a reduced dose by skipping one of the doses.
	Second	Discontinue study drug permanently if the intolerance reoccurs or persists.
Sustained increased systolic (>170 mm Hg) or sustained increased diastolic (>100 mm Hg) blood pressure in a previously normotensive subject	First	
Study drug may be withheld and then restarted at a reduced dose by skipping one of the doses.
 
Irrespective of study drug dose adjustment, subjects who develop a sustained increased systolic (>140 mm Hg) or a sustained increased diastolic (>90 mm Hg) blood pressure should be started on antihypertensive medications (ie, diuretics, calcium channel blockers, ACE inhibitors, etc.) or have their antihypertensive regimen adjusted if already on any antihypertensive agent.

	Second	Discontinue study drug permanently if the hypertension reoccurs or persists.
Intolerable nausea or vomiting	First	Study drug may be withheld and then restarted at a reduced dose by skipping one of the doses.

AE	Occurrence ^b	Action
	Second	Discontinue study drug permanently if the intolerance reoccurs or persists.
QTcF >500 ms for female subject OR >480 ms for male subject, at any time point	-	
The ECG should be repeated as triplicate (all three within 2 minutes) and a cardiology consult may be obtained as medically necessary.
 
 • If the repeat ECG confirms QTcF >500 ms (females) or >480 ms (males), dosing must be interrupted for up to 14 days • If the QTcF resolves to ≤480 ms (males and females)/they may resume dosing at the reduced dose by skipping one of the doses (ie, morning or evening) • If the QTcF remains >480 ms (males and females) after 14 days of dose interruption, the study drug must be permanently discontinued.
QTcF change of >30 ms from baseline	-	If the QTcF has increased >30 ms when compared to the baseline with no other known etiology, and the PI considers it clinically significant then a confirmatory ECG (single) will be performed and dose should be reduced by skipping one of the doses (ie, morning or evening) for the remainder of the study.

Abbreviations: ACE, angiotensin-converting-enzyme; AE, adverse event; ALP, alkaline phosphatase; ALT, alanine aminotransferase; ANC, absolute neutrophil count; AST, aspartate aminotransferase; csDMARDs, conventional synthetic disease-modifying antirheumatic drugs; ECG, electrocardiogram; MOA, mechanism of action; PI, principal investigator; QTcF, QT interval correction for heart rate (QTc) using Fridericia's correction formula; ULN, upper limit of normal

- ^a These are examples based on previously observed AEs for agents with similar MOA (ie, fostamatinib). All other potential/spontaneous Grade 3/4 AEs that can warrant dose reduction or interruption are not excluded and will be assessed on an ongoing basis during the study. Those would be evaluated upon judgment by the principal Investigator and the safety operations team.
- ^b First/second occurrence relates to AE; abnormalities at repeat tests during monitoring of an AE are considered to belong to the same event (AE).
- c A central laboratory must be used for repeat ALT, AST, ALP or ANC.

Subject Error

If the subject does not take his/her study drug dose at regularly scheduled dosing time, he/she should take the dose as soon as possible but at least 8 hours before the next scheduled dose. If the next scheduled dose is within the 8 hours window, the dose is considered missed, and the subject should resume dosing with the subsequent dose on the original schedule.

If the subject experiences any drug interruption(s) he/she should notify their study site physician during the next scheduled study visit. Such protocol violations may result in data

that are not deemed evaluable (by the investigator) for a protocol analysis and/or may require subject(s) to be discontinued.

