6.4.5.5 Reporting Serious Adverse Events

Any AE that meets SAE criteria (Section 6.4.5.2) must be reported to PPD Pharmacovigilance (PVG) immediately (ie, within 24 hours) after site personnel are aware of the event. This must be done via the eCRFs on the AE page. The entry will automatically be

sent to the PPD PVG team for review. If the eCRF system is unavailable, a manual SAE form may be used and faxed to the numbers outlined below.

The nonserious adverse event of special interest (AESI) defined in Section 6.4.5.6 should be recorded in the eCRF using the same process as for reporting SAEs.

The following contact information is to be used for PPD PVG:

PVG [contact]/[contact]

PVG Fax line: [contact]/[contact] or [contact]

6.4.5.6 Suspected Unexpected Serious Adverse Reactions and Nonserious Adverse Events of Special Interest

The following nonserious AESI should be recorded on the eCRF using the same process as for reporting SAEs.

- **Neutropenia** with fever defined as ANC <1500/mm³ or <1.5 × 10⁹/L on the most recent complete blood count with fever equal to or greater than 38°C that does not fulfill any of the serious criteria, ie, hospitalization.
- **Hepatotoxicity** defined as ALT >3 × ULN plus total bilirubin >2 × ULN that does not fulfill any of the serious criteria, ie, hospitalization. This information should be recorded on the drug induced liver injury eCRF each time the elevated laboratory parameters are met during the study.

Oscotec Inc. will promptly evaluate all suspected unexpected serious adverse reactions (SUSARs) and nonserious AEs of special interest against cumulative product experience to identify and expeditiously communicate possible new safety findings to Investigators, institutional review board (IRBs)/independent ethics committee (IECs), and applicable health authorities based on applicable legislation.

To determine reporting requirements for single AE cases, Oscotec Inc. will assess the expectedness of these events using the study drug Investigator's brochure. Reporting requirements will also be based on the Investigator's assessment of causality and seriousness, with allowance for upgrading by Oscotec Inc. as needed.

Osco Inc. will compare the severity of each SUSAR and the cumulative event frequency reported for the study with the severity and frequency reported in the applicable reference document.

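### Table 3-1, liver row: an asymptomatic ALP still above 5 × ULN on a stable or lower repeat meets both the continue bullet and the withhold bullet, and the row does not say which prevails

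*Protocol*

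**What the plan says.** Protocol Section 3.1.1, Table 3-1, has one row for liver enzymes. A subject enters it through either of two criteria:

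- ALT/AST: "ALT or AST elevations (range 3 to 5" × ULN), a range with an upper end.
- ALP: "or ALP $>3 \times$ ULN and $>2 \times$ baseline", with no upper end.

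For a first occurrence there are three bullets:

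- Bullet 1: if there are no symptoms, repeat within 72 hours "and, if stable or lower, may continue dosing of study drug". No maximum value is stated.
- Bullet 2: "If on repeat test value has increased further but remains" below 5 × ULN without symptoms, withhold study drug, retest weekly, and resume once the value has stabilized below 5 × ULN.
- Bullet 3: if there are symptoms or the value is above 5 × ULN, "withhold csDMARDs and study drug". Follow weekly until symptoms abate and values are back at baseline. csDMARDs may then restart at the prior dose, and study drug may restart with one of the two daily doses skipped.

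**The concern.** Bullets 1 and 3 lead to very different management. Under bullet 1 the subject stays on full study drug and background therapy. Under bullet 3 both stop, and study drug may return only at half the daily dose once values are back at baseline. If one ALP result satisfies both bullets, two sites acting in good faith could treat the same subject differently.

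Liver enzyme change is a named potential risk of the drug (Section 1.5), and 400 mg BID had not been given to humans before (Section 1.3). There is no safety monitoring committee (Section 6.7) and no external data monitoring committee (Section 11.1.1) that would align site practice. What is at stake is consistent dosing and safety handling in a few subjects, not a statistical quantity.

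**Working it through.** The plan gives no figure to reproduce here, so the check sets the conditions of the row against one another.

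**Inputs (Table 3-1).** Let *f* be the first value and *r* the repeat, both in multiples of ULN.

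- Entry: ALT/AST 3 ≤ *f* ≤ 5; ALP *f* > 3 and more than twice baseline (taken as met below).
- Bullet 1: asymptomatic and *r* ≤ *f* (taking stable or lower as not increased).
- Bullet 2: asymptomatic, *r* > *f* and *r* < 5.
- Bullet 3: symptomatic, or above 5. The row does not say whether *f* or *r* is meant.

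**Cases.**

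| Enzyme, *f* → *r* | Symptoms | Bullets met now | Under the fix below |
|---|---|---|---|
| ALP 6.0 → 5.8 | no | 1 and 3 | 3 |
| ALP 6.0 → 6.0 | no | 1 and 3 | 3 |
| ALP 6.0 → 7.0 | no | 3 | 3 |
| ALP 6.0 → 4.5 | no | 1 only if bullet 3 reads *r*; 1 and 3 if it reads *f* | 1, unless the sponsor's clinicians decide otherwise |
| ALT 4.0 → 4.0 | no | 1 | 1 |
| ALT 4.0 → 4.5 | no | 2 | 2 |
| ALT or ALP 4.0 → 5.0 | no | none | 2 |
| ALT 4.0 → 5.0 | yes | 3 | 3 |
| ALT 5.0 → 5.0 | no | 1 | 1 |

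**Overlap.** It needs *r* ≤ *f* together with *r* > 5, hence *f* > 5. ALP allows this. It holds whether bullet 3 is read on the first value, the repeat, or either, because both exceed 5. For ALT/AST entry stops at *f* = 5, so a stable or lower repeat cannot exceed 5 and there is no overlap.

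**Gap.** An asymptomatic rise to exactly 5.0 fails bullet 1 (it rose), bullet 2 (not below 5) and bullet 3 (not above 5).

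**Can the overlap case occur?** Inclusion criterion 6 (Section 4.1.1) limits creatinine, ALT, AST and bilirubin but sets no ALP limit. If baseline ALP is 2.5 × ULN or more, twice baseline is at least 2 × 2.5 = 5 × ULN. Every ALP value that brings such a subject into the row is then above 5, and an unchanged asymptomatic repeat meets both bullets.

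**Does other text settle it?**

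- Footnote b treats repeat abnormalities as the same event, so the second-occurrence rule does not apply.
- Footnote a leaves other events to judgment ("All other potential/spontaneous Grade 3/4 AEs that can warrant dose reduction or interruption are not excluded") but sets no order among the bullets.
- The Note in the row depends on ALT with bilirubin: "Discontinue study drug permanently if the ALT elevation is accompanied by an elevation in direct bilirubin".
- The hepatotoxicity event of special interest in Section 6.4.5.6 is "defined as ALT >3 × ULN plus total bilirubin >2 × ULN", again not ALP.
- Section 6.4.4 names outside guidance for assessing liver tests but states no dosing rule.
- Section 4.2.1, item 4, permits withdrawal for laboratory changes but does not require anything.

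**The case against.** The best defence is that the two bullets do not truly contradict each other. Bullet 1 is a permission and bullet 3 is a command, so a site that withholds breaches nothing. Bullet 2 supports this: its wording, "If on repeat test value has increased further but remains", assumes a value that started below 5 × ULN. Bullets 1 and 2 then read naturally as the pathway below 5, and bullet 3 as the pathway above 5 or with symptoms. The table is also titled as guidelines, and footnote a calls its entries examples.

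Most of this stands, and it is why the point is minor. But the division at 5 × ULN is an inference that the reader has to make. Read in sequence, the bullets can equally be taken as outcomes of the repeat test (not higher; higher but below 5; above 5), and a stable ALP of 6.0 × ULN then stops at bullet 1.

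The defence is stronger on the boundary value. For a rising asymptomatic result, bullet 2 just below 5 and bullet 3 just above 5 both withhold study drug. Only csDMARD interruption and the restart rule are left open, at one exact value.

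**Conclusion.** The point holds as a minor drafting conflict between two stated dosing rules, confined to asymptomatic subjects whose ALP is still above 5 × ULN on a stable or lower repeat. The gap at exactly 5.0 × ULN is a lesser point and also applies only to asymptomatic subjects. Both follow from the literal text, taking stable or lower to mean not increased. The number of subjects affected cannot be derived from the documents and is probably small. No sample size, power, alpha or endpoint figure changes.

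A reader might infer more than the documents support:

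- *ALT and AST have the same conflict, or no instruction above 5 × ULN.* They do not conflict, because entry stops at 5 × ULN. Bullet 3 itself states the action above 5, so the capped heading is a mismatch, not a missing rule.
- *A subject at exactly 5.0 × ULN is left with no instruction.* Not if symptomatic (bullet 3) or unchanged (bullet 1), and study drug is withheld on either side of the value for a rising result.
- *Any first value above 5 × ULN should trigger bullet 3.* The row does not say which value counts. Interrupting treatment for an ALP that falls from 6.0 to 4.5 would be a clinical policy choice that nothing in the protocol supports.
- *Sites will in fact dose differently.* That is possible, but the documents do not show it; many would take the stricter bullet.

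**What to change.** Change the first-occurrence cell of the liver row in Table 3-1:

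- Bullet 1: add that the repeat value must be at or below 5 × ULN.
- Bullet 2: replace below 5 with at or below 5 × ULN, both in the condition and in the restart rule.
- Bullet 3: state that it governs whenever the repeat value is above 5 × ULN or the subject is symptomatic.

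Each combination of first value, repeat value and symptoms inside the row then leads to one bullet. The sponsor's clinicians should decide, and write down, whether a first value above 5 × ULN that falls to 5 or below on repeat also goes to bullet 3. Footnote b and the second-occurrence cell can stay as they are.

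The cost is wording in one table row, with no extra tests or subjects. The downside is that a few asymptomatic subjects with stable ALP above 5 × ULN would have study drug and csDMARDs interrupted, which is what bullet 3 already commands on its own terms. This is a cheap improvement.
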